## **METHODS: PARTECIPANTS, INTERVENTIONS, OUTCOMES**

**9. Setting:** IRCCS Fondazione Policlinico Universitario A. Gemelli (Promoter Coordinating Centre), Centro Cardiologico Monzino IRCCS, IRCCS Policlinico San Donato

**Number of patients enrolled:** The study will include 180 patients (expected 60 patients per center, but enrolment is competitive) aged >18 years hospitalized for MINOCA.

### **10. Inclusion criteria:**

- Ability to give informed consent to the study
- Age > 18y
- MINOCA diagnosis, defined as:
  - Acute myocardial infarction (based on Fourth Universal Definition of Myocardial Infarction Criteria):
  - Evidence of non-obstructive coronary artery disease on angiography (i.e., no coronary artery stenosis >50%) in any major epicardial vessel.
  - No specific alternate diagnosis for the clinical presentation (i.e. non-ischemic causes of myocardial injury such as sepsis, pulmonary embolism, and myocarditis).

### **Exclusion criteria:**

- Inability or limited capacity to give informed consent to the study
- Age < 18 y
- Pregnant and breast-feeding women or patients considering becoming pregnant during the study period will be excluded. For women of childbearing potential, the use of a highly effective contraceptive measure is required in order to be included in the study. “Highly effective contraceptive” is defined in accordance with the recommendations of the Clinical Trial Facilitation Group as a contraceptive measure with a failure rate of less than 1% per year ([https://www.hma.eu/fileadmin/dateien/Human\\_Medicines/01-About\\_HMA/Working\\_Groups/CTFG/2020\\_09\\_HMA\\_CTFG\\_Contraception\\_guidance\\_Version\\_1.1\\_updated.pdf](https://www.hma.eu/fileadmin/dateien/Human_Medicines/01-About_HMA/Working_Groups/CTFG/2020_09_HMA_CTFG_Contraception_guidance_Version_1.1_updated.pdf)).
- Alternate diagnosis for the clinical presentation (i.e. non-ischemic causes of myocardial injury such as sepsis, pulmonary embolism, valve disease, hypertrophic cardiomyopathy and myocarditis). Also patients presenting with Takotsubo syndrome will be excluded.

- Contraindication to contrast-enhanced CMR, eg, severe renal dysfunction (glomerular filtration rate <30 mL/min), non-CMR-compatible pacemaker or defibrillator.
- Contraindication to drugs administered: e.g a history of hypersensitivity to drugs administered or its excipients, significant renal and/or hepatic disease.
- Patients with comorbidities having an expected survival <1-year will be excluded.

### **Withdrawal criteria :**

Subjects may be withdrawn from the study at discretion of the Investigator if one of the following criteria applies:

- Patients voluntary to stop participate to the study protocol.
- Progression of patient's disease or need to change medical therapy.
- Intolerable adverse effects. Pregnancy or intention of becoming pregnant at any time of the study.. Patients enrolled will have to communicate to the investigator if they get pregnant at any time of the study to be excluded by the study protocol.

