***T4\_ Follow-up clinical visit at 12 months (365 +/- 5 gg)***

- Personal information: weight, height, BMI
- Collection of ongoing medical therapy
- Compilation of SAQ score
- Collection of MACE at follow-up
- Registration of adverse events

Study Assessment	Screening and randomization	Follow-up phone interview_ T1 (3 months)	Follow-up phone interview_ T2 (6 months)	Follow-up phone interview_ T3 (9 months)	Visit of End of Follow-up (12 months)
Days	0	90 +/- 5 gg	180 +/- 5 gg	270 +/- 5 gg	365 +/- 5 gg
Weeks	0	12	24	36	52

Informed consent	X				
Inclusion criteria	X				
Anagraphic data	X				
Personal information (weight, height,BMI)	X				X
Clinical history	X				
Clinical examination	X				
Vital signs	X				
Ongoing medical therapy (concomitant medications included)	X	X	X	X	X
Patients assigned to "Standard approach"	X				
ECG features	X				
Transthoracic Echocardiography	X				
Coronary angiography and ventriculography	X				
CMR with contrast media (if clinically indicated)	X				
Laboratory data (creatinine, full blood count, Troponin I peak, CK-MB peak, NTproBNP, CRP)	X				
Patients assigned to "Precision-medicine approach"					
OCT (if coronary plaque rupture/erosion is suspected)	X				
	X				

Acetylcholine provocative test (to assess the presence of coronary vasospasm)					
TE-Echo and/or CE-Echo (if distal/microvascular embolization is suspected)	X				
CMR with contrast media (if clinically indicated)	X				
Blood sampling for circulating biomarkers and miRNA expression profile	X				
Collection of MACE	X	X	X	X	X
Adverse events	X	X	X	X	X
SAQ score					X

SAQ score:

1. The following is a list of activities that people often do during the week. Although for some people with several medical problems it is difficult to determine what it is that limits them, please go over the activities listed below and indicate how much limitation you have had **due to chest pain, chest tightness, or angina over the past 4 weeks.**

Place an x in one box on each line.

Activity	Severely Limited	Moderately Limited	Somewhat Limited	A Little Limited	Not Limited	Limited, or did not do for other reasons
Dressing yourself						

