### *Definition of the MACE*

MACE analysis includes:

- All cause death:
  - Cardiac death (in which a direct cause attributable to cardiac disease is present);
  - Sudden cardiac death (in which cardiac death occurred out of the hospital and suddenly; or in the hospital due to ventricular arrhythmias unrelated to other concomitant cardiac conditions);
  - Non-cardiac death (in which the event of death is considered not to be a direct consequence of cardiac disease);
- Hospitalization in which the main diagnosis is myocardial infarction, stroke or heart failure;
- Repeated coronary angiography.

The analysis will consider time to first event and time to each event.

Safety parameters will include data deriving from history and physical examination performed at each visit, laboratory data and results of functional and imaging tests. To enhance detection of adverse events between visits, all patients will be encouraged to contact the research team at any time with concerns or any perceived changes in their healthcare status.

**14. Sample size calculation:** Sample size calculation for the primary endpoint: to detect a mean group difference of change in SAQ score of 9 U, we calculated that a sample size of 70 patients per group (140 patients total) gave 80% power to detect a between-group difference in SAQ. This

calculation assumed a 2-tailed 5% significance level. This projected calculation assumed an SD of 19 U and was consistent with previous studies (see landmark CorMicA trial). However, we extended the sample size at 180 patients to avoid any reduction of statistical power due to patients lost at follow-up or due to poor compliance to medical therapy.

**15. Timeline:** At 36 months all patients will be enrolled and will have completed the follow-up. The study will be considered ended after the date of last patient last visit (LPLV). Blood samples will be analysed for assessment of circulating biomarkers and miRNA to detect associations with specific mechanisms underlying MINOCA, for stratification of prognosis and to evaluate response to medical therapy. Furthermore, CMR sequences will be analysed to detect functional and structural characteristics associated with specific mechanisms underlying MINOCA and with for stratification of prognosis.

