## **METHODS: INTERVENTION ALLOCATION**

### **16-17 Randomization**

Trained staff in the catheter laboratory will use a web-based randomization tool, available 24h/24h at any of the enrolling sites, to immediately randomize the patient after the index coronary angiography revealing non obstructive CAD, to “precision medicine approach” versus “standard approach” (open label approach: both patients and physicians will know the allocated treatment arm).

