## **METHODS: DATA COLLECTION, MANAGEMENT AND ANALYSIS**

**18. Data collection:** Data collection will be carried out through an electronic CRF (eCRF). The investigator or an authorized member of the investigation team must sign all completed eCRFs with a digital signature (a password will be provided by the data management center at the start of the study). The management of clinical data will be carried out in accordance with the data cleaning procedures, both for the data recorded in the eCRFs and from other sources. Appropriate computerized software will be used to verify the accuracy of the database. Investigators will be asked for incomplete, inconsistent or missing data.

**Source Documents (SDs):** Investigators have to maintain information in the patient's medical record that corroborates the data collected in the eCRF. To meet these demands, the following is a list of information that must be recorded and shown to monitors and regulatory inspectors as needed: Clinical history / physical condition of the participant before inclusion in the study with sufficient detail to verify the inclusion and exclusion criteria; clinical notes dated and signed on the day of entry into the study, protocol number, clinical site, number assigned to the patient and a declaration certifying the signature of the informed consent; record of abnormal laboratory tests; reported adverse events and their resolution; including supporting documents such as discharge sheet, catheterization reports, ECG, echocardiography and CMR reports; laboratory results; condition of the patient upon completion or withdrawal from the study.

**Case Report Form:** All requested data will be carefully recorded by authorized personnel documented in the Authorized signature log in the eCRF.

**19. Confidentiality:** All data and information collected during this study concerning the participant must adhere to the privacy protection standards, based on the application of the Italian laws on the

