## **20. Statistical analysis**

The study population will comprise participants who had provided informed consent. There will be no interim analyses, and the trial enrolment will be considered complete after the pre-specified recruitment target was met. Data will be reported as mean  $\pm$  SD, median (25th, 75th percentile), or frequency and percentage. Continuous outcome measures recorded at baseline and 6 months will be compared between randomized groups using a mixed effects linear regression model, including a random effect for patients, and fixed effects for time point (baseline or follow-up), randomized group, and their interaction. The baseline-adjusted intervention effect will be estimated as the interaction term from this model. Categorical outcomes will be compared between randomized groups using Fisher exact tests with additional calculation of relative risk estimation of effect size. We will perform 2-tailed analysis and considered a p value  $\leq 0.05$  to be significant. Statistical analyses will be performed using SPSS program.

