## **26. Patient Information and Informed Consent and Consent to the Processing of Personal Data**

The PIs of each clinical site will explain to patients the nature of the study, its rationale, the procedures involved, the duration, the potential risks and benefits, and any possible inconvenience both orally and by means of a written form (Patient Information: Each patient will be informed about the voluntary participation in the study and the possibility, at any time, to withdraw from the study without incurring any deterioration in the quality of medical assistance and treatments. The patient's data will be anonymized after the withdrawal of informed consent and the patient will be informed about any alternative treatments. Patients should be informed that other authorized individuals, in addition to their doctor, may review their personal data and will issue a consent to the processing of personal data in this regard. All study participants will be provided with sufficient information to make an informed decision about participating in the study. They will be given the opportunity to discuss treatment options and participation in the study with relatives or other trusted persons. The patient information sheet, the consent form and the consent form for the processing of personal data will be submitted to the respective CEC and the competent authorities (OsSC) for review and approval. The participant's formal consent, accompanied by the appropriate approved forms, must be obtained before submitting the participant to any procedure. Participants should read and consider the information received before dating and signing the consent form and attached forms, a copy of which will be provided to them. The consent form and the attached forms will also be signed by the investigator (or his delegate) and will be kept in the official documents of the study.

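### An investigator who knows the arm may withdraw a patient from the study for progression or a therapy change, and nothing keeps the only scheduled SAQ (month 12) for that patient

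*Combined protocol and SAP*

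**What the plan says.** The withdrawal criteria (within section 10) open with "Subjects may be withdrawn from the study at discretion of the Investigator if one of the following criteria applies". One criterion is "Progression of patient's disease or need to change medical therapy". Leaving at the patient's own wish is a separate criterion, so this one does not depend on the patient wanting to stop. What is left is the study, not a drug.

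Sections 16-17 describe an "open label approach: both patients and physicians will know the allocated treatment arm".

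The primary endpoint in section 12 is the SAQ at one year. In the study timeline, "Compilation of SAQ score" appears only under the 12-month visit (T4), and the assessment table marks the SAQ in that column alone.

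On what follows a withdrawal, two places come near. Section 18 wants the source documents to hold the "condition of the patient upon completion or withdrawal from the study". Section 26 says the patient's "data will be anonymized after the withdrawal of informed consent". Neither says whether the T1 to T4 contacts or the 12-month SAQ go ahead after a withdrawal decided by the investigator.

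Section 20 compares continuous outcomes "using a mixed effects linear regression model, including a random effect for patients", at baseline and 6 months, and names no method for a missing SAQ. Section 14 raises the sample from 140 to 180 to protect power against losses "due to patients lost at follow-up or due to poor compliance to medical therapy". Section 11.b foresees dose changes when the disease worsens, and the text just before it lets any drug of the same class be used.

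**The concern.** Worsening disease and a need for other therapy are close to angina status and quality of life. If such patients leave and contacts stop, whether a 12-month SAQ exists depends on how the patient is doing. The person deciding knows the arm, and the arms use different drugs by design (section 11a), so reasons to change therapy can differ between them.

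The bias can run either way. More withdrawals of patients doing badly under standard care would shrink a true benefit; more in the precision arm would inflate it. The mixed model cannot borrow from earlier scores, because no SAQ is scheduled before month 12. The 40 extra patients restore numbers, not comparability.

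MACE is exposed as well. A first event after withdrawal for symptoms or a therapy change would be missed, and so would later events, although the MACE definition plans an analysis of time to each event.

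Section 11.b and the withdrawal criteria can be read together, but neither says whether a dose change or a same-class switch counts as a therapy change that permits withdrawal.

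**Working it through.** **Inputs from section 14.** Difference 9 U, SD 19 U, two-sided 5%, 80% power, 70 per group, extended to 180 in total (90 per arm with 1:1 allocation).

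**Inputs that are assumptions.** The withdrawal rate in each arm, and the odds ratio (OR) of withdrawal per SD worse 12-month SAQ, taken as 1.25, 1.5, 2 and 3.

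**The plan's own figure.** With 70 per arm, SE = 19 × √(2/70) = 3.21 and power = Φ(9/3.21 − 1.96) = 80.0%, as stated. With 90 per arm and no loss, SE = 2.83 and power is 88.8%. The enlargement covers a loss of 40/180 = 22.2%, if the loss is unrelated to outcome.

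**Model.** In each arm the standardised score is z ~ N(0,1), and P(withdrawn) = expit(a − ln(OR) × z), with a set to give that arm's rate. Then:

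- observed difference = 9 + 19 × (mean z kept in precision − mean z kept in standard);
- power by normal approximation, using the SDs and numbers of the patients kept.

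**One line worked.** Standard 15%, precision 5%, OR 2:

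- Mean z kept is 0.0978 (standard) and 0.0338 (precision), so the difference is 9 + 19 × (0.0338 − 0.0978) = 7.78 U.
- The SDs of those kept are 18.50 and 18.80 U, with 76.5 and 85.5 patients, so SE = √(18.50²/76.5 + 18.80²/85.5) = 2.93.
- Power = Φ(7.78/2.93 − 1.96) = 75.6%.

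**All results** (observed difference; power in the first two scenarios, error rate in the third):

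| OR | Standard 15%, precision 5% | Standard 10%, precision 5% | Standard 5%, precision 15%; error if no true effect |
|---|---|---|---|
| 1.25 | 8.58 U; 82.0% | 8.79 U; 84.8% | 9.42 U; 5.2% |
| 1.5 | 8.25 U; 79.4% | 8.62 U; 83.7% | 9.75 U; 5.7% |
| 2 | 7.78 U; 75.6% | 8.38 U; 82.4% | 10.22 U; 7.0% |
| 3 | 7.27 U; 71.6% | 8.11 U; 81.2% | 10.73 U; 9.3% |

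With the same losses and no selection, power is 85.3% in the first scenario and 86.3% in the second. In the third, with no true effect, the false difference is 0.42 to 1.73 U.

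**Cases with little or no bias.**

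- Equal 10% rates with equal selection: 9.00 U at every OR.
- One common rule on the absolute score, 10% of the standard arm withdrawn (9.1% to 6.5% of the precision arm): 8.96, 8.88, 8.69 and 8.38 U; power 85.4% to 83.6%.
- The same rule with 20% of the standard arm withdrawn (18.4% to 13.8% of the precision arm): 8.93, 8.79, 8.47 and 7.98 U; power 81.2% to 77.8%.

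**A harsher set of assumptions, by a simpler formula.** If a share q is withdrawn and those patients average m below their arm's mean, the mean of those kept rises by m × q/(1 − q). Take 10% withdrawn in precision and 20% in standard. With m = 19 U the rises are 2.11 and 4.75 U, so 9 U is seen as 6.36 U (power 54%, SD 19). With m = 9.5 U it is seen as 7.68 U (power 70%).

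**The case against.** The strongest reply is that the withdrawal criteria are read too harshly. They are permissive. The T1 to T4 contacts all record current therapy, which is the natural place to note a change in a patient still being followed. Section 11.b expects dose changes on worsening. Rehospitalisation and repeat angiography are endpoints, and an analysis of time to each event needs follow-up beyond the first. All this suggests that progression was not meant to end follow-up. That is fair, but it shows a tension with the withdrawal criteria and does not override them.

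Section 12 also has two blinded cardiologists from an external unit handle the questionnaires. That limits assessment bias; it does not decide who reaches month 12.

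The sizes rest wholly on assumed rates and selection, and many scenarios are mild. This stands. At 10% against 5%, power stays above the planned 80% throughout. The 9.3% error needs a threefold gap between arms, OR 3 and no true effect, and nothing in the documents points to that combination. The loss of MACE is not quantified.

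The lack of an earlier SAQ and of a missing-data method would affect any lost patient, whatever the withdrawal criteria say. This is true, but the withdrawal rule adds losses that the trial itself creates.

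Finally, section 32 refers to attached consent files that were not part of the text examined. A term on follow-up could be there.

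**Conclusion.** The concern holds. As written, an investigator who knows the arm may end a patient's participation on grounds close to the outcome, and nothing in the text examined keeps the later contacts or the one scheduled SAQ. The gap in wording is certain; its effect is not, because the documents do not say how often the rule will be used or how selectively.

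Under equal rates with equal selection there is no bias. Under a common rule or weak selection the effect is small. It becomes material when rates differ by arm and selection is stronger: at 15% against 5% with OR 2 to 3, a true 9 U is seen as 7.8 to 7.3 U and power is 76% to 72%. The reverse imbalance gives 10.2 to 10.7 U, or an error of 7.0% to 9.3% if there is no effect. These figures tie withdrawal to the score the patient would have had at 12 months; a looser link corresponds to the lower ORs. Therapy changes driven by the arms' different drugs need not follow this pattern.

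The plan should be changed, because a 12-month SAQ that was never collected cannot be recovered at analysis.

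**What to change.** Add to the withdrawal criteria that disease progression, or a change or stop of study therapy, does not by itself end study follow-up. Such patients keep the T1 to T4 MACE contacts and the 12-month SAQ unless they withdraw consent, and they are analysed in the arm to which they were allocated.

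Reconcile the criterion with section 11.b and with the same-class sentence before it, stating whether a dose change or a same-class switch counts as a therapy change. This concerns data collection and analysis only. Treatment decisions, and the adverse-effect and pregnancy provisions, remain with the sponsor, who should state whether patients withdrawn on those grounds still give a 12-month SAQ.

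Some SAQs will still be missing. Section 20 should therefore name a method for them with a sensitivity analysis, and withdrawals should be reported by arm and reason.

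The cost is protocol wording, plus calls and a 12-month visit that are already scheduled, for a few more patients.

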### **Stopping rules**

Premature termination of the clinical trial could be considered if the sponsor believes that it is necessary to terminate the clinical trial as a result of the observed efficacy of the treatment (benefit), of a likelihood of failing to reject the null hypothesis (futility), evidence of severe adverse effects of treatments administered (harm) or when the clinical trial proved to be impracticable (e.g difficulty in patients enrolment).

### **11a. Intervention(s):**

Patients with myocardial infarction undergoing to clinically indicated coronary angiography will be asked to sign the informed consent to the study before the coronary angiography/ventriculography and enrolled only after MINOCA diagnosis. MINOCA patients will be then randomized 1:1 (using an online software available 24h/24h) to:

**A. "Precision medicine approach"** consisting of:

*Comprehensive diagnostic work-up with:*

- Coronary angiography and ventriculography in all patients
- OCT (if coronary plaque rupture/erosion is suspected) at the time of coronary angiography in the cath-lab.
- Acetylcholine provocative test (to assess the presence of coronary vasospasm) at the time of coronary angiography in the cath-lab.
- TE-Echo and/or CE-Echo (if distal/microvascular embolization is suspected) during the hospitalization at the echo laboratory
- Blood sampling for circulating biomarkers and miRNA expression profile at the time of coronary angiography or within 12 hours from coronary angiography. Blood sampling will be processed and analysed in the research laboratory of the Department of Cardiovascular Science. Biological aliquots will be preserved at XBiogem Biobank at Fondazione Policlinico Universitario A. Gemelli IRCCS, Rome.
- Trans-thoracic echocardiography in all patients during the index hospitalization
- CMR in all cases during the index hospitalization.

*Targeted pharmacological treatment specific for the underlying cause:*

- DAPT ± stent implantation (if required), statins, beta-blockers, ACEi/ARB (in case of evidence of plaque rupture/erosion)
- CCB and/or nitrates (in case of documentation of coronary vasospasm)
- Anticoagulation (in case of coronary embolism).

**B. "Standard approach"** consisting of:

*Routine diagnostic work-up with:*

- Coronary angiography and ventriculography
- Transthoracic echocardiography in all patients during the index hospitalization
- CMR with contrast media only if clinically indicated (i.e. to exclude myocarditis or takotsubo syndrome)

*Standard medical treatment with:*

- DAPT in all patients
- Beta-blockers (if indicated by the clinical context, i.e. documentation of left ventricular ejection fraction <50%, tachycardia).

- High intensity statins in all patients
- ACEi/ARB (if clinically indicated).

Pharmacological strategy will be started after the coronary angiography during the index hospitalization. All the procedures will be done by cardiologists with experience in the specific field. All three enrolling centers already have a high proficiency in performing all the procedures required for this study.

